# 2.0 IRB Review History. Approved by the IRB on 2/23/2018

# 3.0 Background information and specific aims

Type 2 diabetes (T2D) is an epidemic in the United States, affecting 29.1 million people. Poor glycemic control contributes to vascular complications of T2D (retinopathy, heart and kidney disease, stroke, and amputation) but recent clinical trials (ACCORD, ADVANCE, VADT) testing the potential benefits of aggressive medication management have been mostly neutral or negative. These trials targeted hemoglobin A1c (HbA1c) concentrations. However, there is growing evidence that glycemic variability (GV; from hyperglycemic peaks to hypoglycemic nadirs) may be a better treatment target than HbA1c. Although GV in early T2D is driven primarily by postprandial glycemic excursions, the results of dietary interventions to limit postprandial excursions have been mixed, perhaps because they used one-size-fits-all strategies such as low glycemic load (GL) diets that ignored the fact that individuals vary greatly in their glycemic response to food.

Several recent studies show that the composition and functional potential of the intestinal microbiota are critical factors in alucose homeostasis. With the Personal Nutrition Project (PNP); http://newsite.personalnutrition.org/WebSite/Home.aspx, [name] et al. devised the first personalized algorithm for predicting glycemic response to food. Using a machine learning approach, they developed a multidimensional profile that predicted food-specific glycemic excursions from gut microbiome data, various blood tests, questionnaires, and one week of mobile monitoring of food intake, glycemia, sleep, medication, physical activity, stress, and hunger. Subsequently, in a randomized trial among Israeli prediabetic individuals, the investigators successfully shown that tailored dietary recommendations from PNP algorithm were successful in reducing postprandial glycemic excursions.

[name] team at New York University School of Medicine will conduct an initial validation study of the PNP algorithm in a North American population with recently diagnosed T2D or pre-diabetes. This will be accomplished in a 2-stage, single-group feeding study in 20 individuals, including 10 participants managed with lifestyle alone, and 10 managed with lifestyle plus metformin.

# 4.0 Background

According to the Centers for Disease Control and Prevention, 29.1 million people in the US (9.3% of the population) have diabetes 1. Diabetes is the most costly chronic disease in the US; with expenditures reaching \$245 billion in 20122. Between 2005 and 2050, the prevalence of diabetes is expected to double3. Patients with T2D are at increased risk of a variety of vascular complications, including heart and kidney disease, stroke, retinopathy, and amputation. Numerous epidemiologic studies show a continuous relationship between HbA1c and microvascular and cardiovascular complications. However the results of intensive glycemia medication management trials (including ADVANCE, ACCORD and VADT) have been largely neutral or negative 4-7 with several possible explanations:

- Interventions were too late in the disease trajectory: These studies were conducted in patients with established T2D who had already developed complications of the disease, limiting the ability of investigators to modify the disease trajectory.
- Reliance on medications: The trials managed glycemia aggressively with medications that increased the frequency of hypoglycemic episodes that, in-turn, increased the risks of cardiovascular disease, allcause hospitalizations, and mortality.
- Poor initial management had long-term effects on subsequent vascular risks: From the point of diagnosis, management of T2D typically involves an incremental regimen that begins with lifestyle

behavior change. The regimen is managed reactively by adding medications when lifestyle efforts fail to achieve an HbA1c of either <6.5% or <7% (depending on the clinical practice guideline embraced by the clinician)  $_{8,9}$ . However, escalation of the medication regimen often is delayed  $_{10}$  and vascular risks resulting from early poor glycemic control appear to be only partially remedied by subsequent better glycemic control. This phenomenon, termed "metabolic memory", appears to involve the accumulation of advanced glycation end-products (AGEs) that result in oxidative stress and inflammation. Accumulation of AGEs and activation of their receptors (RAGE) in-turn, mediate the tissue damage that results in diabetic complications. Activation of the AGE-RAGE pathway also has been shown in animal models to induce injury to pancreatic  $\beta$ -cells11-13. Studies show lower  $\beta$ -cell function to be associated with higher rates of treatment failure, poorer glycemic control, and greater GV in those with T2D, and experimental studies have shown clear metabolic benefits from even minimally preserved  $\beta$ -cell function 14. Consequently, it is important to preserve  $\beta$ -cell function for as long as possible after the diagnosis of T2D is made  $_{15}$  and early management of GV with diet is a potential solution.

The wrong treatment target: ADVANCE, ACCORD and VADT targeted HbA1c, which reflects mean glycemia rather than glucose instability. Titrating medications to HbA1c without addressing postprandial glycemic excursions [which account for about 70% of overall glycemic exposure in patients with early T2D and remaining β-cell function 16] increases the risk of hypoglycemia 17. Compared to a constant high glucose, blood glucose fluctuations are more damaging 18 and appear to result in more pronounced metabolic memory effects19. Recent epidemiologic studies have shown postprandial hyperglycemic peaks to be a powerful predictor of cardiovascular risk, and suggest that GV may be a better treatment target than HbA1c17-22. Several pharmacologic agents are available that limit postprandial hyperglycemia (e.g. insulin, sulfonylureas, acarbose, glinides, DPP-4 inhibitors, and GLP-1 agonists). However, several problems are associated with these medications and they are occasionally prescribed for those with recently diagnosed T2D.

In early T2D GV is driven, primarily, by diet. While there is universal recognition that dietary management is key to successful T2D treatment, there is limited evidence regarding the best dietary approach(es) to take and the results of intervention studies have been mixed. Twelve recent (since 2008) randomized clinical trials of dietary interventions in those with T2D were found in the literature23-33. All used a 1-size-fits-all dietary prescription. However, the impact of diet on glycemia is influenced by many factors, including energy content, and the type and amount of carbohydrates, protein and fat in the meal; as well as how the foods were prepared and cooked. Also, each individual possesses their own unique physiologic response to food, based on their insulin resistance,  $\beta$ -cell function, gastrointestinal factors, and hepatic and peripheral glucose metabolism, which may be influenced by non-dietary factors including sleep, physical activity, medication/supplement regimen, and perhaps others 34, 35. None of the dietary studies that we reviewed tailored counseling to minimize postprandial glycemic excursions. Nearly all evaluated the intervention on the basis of HbA1c but, as discussed above, GV (evaluated in only 1 of the dietary intervention studies) may be a better predictor of downstream complications of the disease 32.

Of particular relevance to managing postprandial glycemia is the innovative work of the Personalized Nutrition Project (or PNP; http://newsite.personalnutrition.org/WebSite/Home.aspx). [name] et al. developed personally tailored double-blinded dietary counseling that lowered postprandial responses in a sample of Israeli individuals with prediabetes 36-38. With our pilot, we intend to validate this tailored approach in a US sample having recently diagnosed T2D. In a future trial, we will combine this tailored approach with our existing behavioral intervention and evaluate its efficacy for reducing GV, and minimizing metabolic memory effects.

#### 5.0. Summary.

T2D poses a significant public health problem. Hyperglycemia is associated with a variety of vascular complications, but clinical trials of medication regimens designed to achieve near-normal HbA1c have been mostly neutral or negative. The lack of benefit observed in these trials may be due to the fact that they targeted HbA1c rather than GV, and were conducted in patients with established T2D that had already

experienced complications of the disease. In early T2D, management of postprandial glycemia may be particular important for minimization of metabolic memory effects and preservation of  $\beta$ -cell function. Postprandial glycemia in early T2D is largely driven by dietary intake, but research that guides clinicians regarding the best dietary approaches to prescribe are mixed. Studies done, to-date, in T2D has used one-size-fits-all dietary regimens that do not take into consideration the person's unique glycemic response to food. The PNP algorithm, which uses a machine learning algorithm to predict postprandial glycemic, may be efficacious for generating tailored dietary advice to moderate the participant's glycemic response to food. However, the PNP algorithm has not been validated in a diverse North American population having T2D.

# 6.0. Inclusion and Exclusion Criteria

# 6.1. Inclusion criteria.

The study will be conducted in a diverse sample of 20 patients with early T2D or pre-diabetes who were managed by lifestyle modification or on metformin. The study inclusion criteria include:

- a. Age >21 years to <70 years
- b. Diagnosed with T2DM within 2 years or pre-diabetes with an HbA1c<8%
- c. Diabetes management by metformin or lifestyle intervention
- d. Willing to use their own or a study loaner smart phone to monitor multiple factors influencing glycemic response to glycemia (e.g., sleep, physical activity, diet, stress, medication, and hunger)

# 6.2. Exclusion criteria.

We will exclude from participation those who:

- a. are unable or unwilling to provide informed consent;
- **b.** are unable to participate meaningfully in an intervention that involves self-monitoring using software available in English (e.g., due to uncorrected sight impairment, illiterate, non-English-speaking, dementia);
- c. are pregnant, are currently trying to become pregnant, or who become pregnant during the study
- **d.** are institutionalized (e.g., in a nursing home or personal care facility, or those who are incarcerated and have limited control over self-management)
- e. have had or are planning to have bariatric surgery during the study
- **f.** have a history of heart disease, kidney disease, or retinopathy (to rule-out those with long-standing, undiagnosed T2D)
- **g.** those with an active infection requiring antibiotics in the last 3 months or who develop an active infection requiring antibiotics during the study;
- **h.** those who use acetaminophen and are unwilling or unable to discontinue its use during the study (acetaminophen affects FGM accuracy)
- i. immunosuppressive drugs within three months prior to participation and
- j. Chronically active inflammatory or neoplastic disease in the three years prior to enrollment.
- k. Patients with known food allergy.

# 6.3. Inclusion of women and minorities.

According to the most recent Behavioral Risk Factor Surveillance System data for adult diabetics in New York City 52.5% are female, 15.6% are Hispanic, 55.3% are non-Hispanic whites, 19.8% are non-Hispanic blacks, 3.4% are non-Hispanic Asians, 5.8% are non-Hispanic other with no data provided on American Indian/Alaskan Natives, or Native Hawaiians or Pacific Islanders. Our targeted/Planned enrollment table combines BRFSS data with local census data, showing that approximately 3.0% of participants will be American Indian/Alaskan Natives and 1.0% will be Native Hawaiians or Pacific Islanders.

Special effort will be made to recruit a sample with a race and gender distribution consistent with New York City's Department of Health rates provided above, with 20-25% of individuals of Latino ethnicity. We have a history of successfully recruiting minorities to our studies. No individual will be excluded from the study on the

basis of race or gender alone. It is possible that the study will have sufficient power to detect differences in intervention effect by gender and race. To our knowledge no research has been published showing a differential effect of interventions such as ours by race or gender.

### 7.0. Study-Wide Number of Subjects.

We will recruit a total of 20 individuals to the study. Preliminary data indicate that we will have access to 200 potentially eligible patients from which we must recruit only 10.0% to enroll 20.

	Sex/Gender							
Ethnic Category	Females	Males	Total					
Hispanic or Latino	2	8	10					
Not Hispanic or Latino	6	4	10					
Ethnic Category: Total of All Subjects *	8	12	20					
Racial Categories								
American Indian/Alaska Native	0	0	0					
Asian	2	4	4					
Native Hawaiian or Other Pacific	0	0	0					
Black or African American	4	6	10					
White	2	4	6					
Racial Categories: Total of All Subjects *	8	12	20					

# 8.0 Study-Wide Recruitment Methods.

Potential participants will be recruited from NYUMLC Endocrinology and print and electronic advertisement. Signed informed consent will be obtained from participants who meet the study eligibility criteria. The following methods will be adopted for the recruitment of eligible participants.

# 8.1. Self-referral from advertisements placed in NYULMC Endocrinology Faculty Group Practices offices.

IRB-approved fliers and brochures containing an overview of the study will be created and displayed in the clinical practice setting for those who may be interested. Interested patients will be provided with the phone number of the investigators that they may call to obtain additional information about the study. Those participants contacting the study office will be provided a brief description of the goals of the study and what their participation would entail. Those who remain interested will be screeened to assure that they meet eligibility criteria using EPIC to verify that their HbA1c levels are <8.0%. We will contact the patients' healthcare provider/agent to determine if their patient is fit to participate in the study. If eligible, a measurement visit is scheduled with the study participant.

# 8.2. Physician referral

During the provision of routine ambulatory care, physicians will identify potentially eligible participants and ask about their interest in a study that proposes to examine dietary patterns that predispose them to postprandial

hyperglycemia. Interested patients will be asked permission (yes/no) for study staff to contact them directly by telephone. Study staff will call patients who agree to be contacted, describe the study, and if the patient expresses an interest, conduct preliminary screening by telephone. Verbal consent is obtained by study staff prior to eligibility screening. Written informed consent will be obtained with a subsequent face to face measurement visit to the CTSI for eligible participants. Alternatively, patients can contact the study staff directly by telephone to discuss possible enrollment.

Interested patients will be provided with the phone number of the investigators that they may call to obtain additional information about the study. Those participants contacting the study office will be provided a brief description of the goals of the study and what their participation would entail. Those who remain interested will be screened to assure that they meet eligibility criteria and schedule a measurement visit.

## 8.3 Self-referral from print and electronic media advertisement

IRB-approved advertisement containing an overview of the study will be created and displayed in newspapers and electronic media. Our contact information will be provided for potential participants to call for information and pre-screening. All self-referring subjects that are not NYLMC patients will be asked to sign a release of information form authorizing the study team to contact their treating physician. The study PI will send the PA a patient participation approval form for the PA to sign whether they PA agree that the patient can enroll a weight loss and brisk walking intervention. Self-referred patients from media outlets will undergo an eligibility visit test (refer section 11.1) to confirm eligibility prior to the baseline measurement visit.

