# 10.0. Study Endpoints

We will validate the PNP algorithm for North American T2D and pre-diabetes patients in a 2-stage, repeated measures quasi-experimental trial in which participants serve as their own control. In stage 1, PNP methods will be used to conduct metabolic profiling and develop a patient-specific algorithm that predicts glycemic responses to food (iAUCpred). In stage 2, participants will consume, for 6 days, isocaloric diets (breakfast, lunch, dinner, and 2 snacks), which will be prepared and delivered daily, including 2 days each of low, moderate, and high glycemic load (GL) foods.

**10.1. Specific aim 1.** We will characterize iAUCpred and iAUCobs and describe differences between the two. Prior studies suggest that any difference between two AUCs less than  $\delta = 30\%$  of iAUCobs is not important and will be considered equivalent. Thus we will describe the equivalence of iAUCpred and iAUCobs by testing the null hypothesis of non-equivalence: H0:  $|iAUC_{pred} - iAUC_{obs}| \ge \delta$  and the alternative hypothesis of equivalence is H1: H0:  $|iAUC_{pred} - iAUC_{obs}| \le \delta$  overall and within each race/ethnicity. **10.2. Specific aim 2**. We will describe the extent to which the equivalence of iAUCpred and iAUCobs differs by whether or not the participant is prescribed metformin.

**10.3. Specific aim 3.** In preparation for future grant applications, we will establish the feasibility and acceptable of the research protocol.

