Subsequently, for the next 6 days, participants will be instructed to follow their normal daily routine and dietary habits, except for the first meal of every day (hereafter referred to as the "test meal".) Test meals consist of one of three different types of standardized meals – each consisting of 50 g of available carbohydrates, given twice to each participant (110 g white bread, 110 g white bread and 30 g of butter, 50 g glucose. Participants will be instructed to enter foods (test and other meals), and amounts consumed into the PNP app (**Day:2-Day:7**). Participants also will be instructed to wear a Fitbit device that streams data on physical activity and sleep to the participant's smart phone (by FitBit app). A follow-up phone call (Telephone-3) to the subject will be made by the study personnel to check that the subject has been able to use the Abbott FGM, PNP app without any issues and let the subject know that the test meals for the next 3 days (**Day:5-Day:7**) will be home delivered. Any adverse events or device incidents will be recorded.

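### Section 8.3 has the treating physician of outside media self-referrals approve a weight-loss and walking intervention that is not part of this protocol

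*Protocol*

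**What the plan says.** Section 8.3 of the protocol sets out recruitment through newspapers and electronic media. It first obtains permission to contact the outside physician: "All self-referring subjects that are not NYLMC patients will be asked to sign a release of information form". The principal investigator then sends an approval form, on which the physician signs whether they "agree that the patient can enroll a weight loss and brisk walking intervention". The section closes by sending media self-referrals to an eligibility visit before the baseline measurement visit.

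The study itself is described differently. Section 3.0 calls it a "2-stage, single-group feeding study in 20 individuals". In stage 1 (section 11.1), "participants will be instructed to follow their normal daily routine and dietary habits, except for the first meal of every day", and that first meal is one of three standardized loads: "110 g white bread, 110 g white bread and 30 g of butter, 50 g glucose". In stage 2 (section 10.0), "participants will consume, for 6 days, isocaloric diets", "including 2 days each of low, moderate, and high glycemic load (GL) foods". Section 6.2 also excludes "those who use acetaminophen and are unwilling or unable to discontinue its use during the study".

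**The concern.** The sentence in section 8.3 is an operating instruction, not background. It says what an outside physician is asked to agree to before the patient enrols. If it is followed as written, the physician considers a weight-loss and exercise program, while the patient is given carbohydrate test meals, a fully provided diet that includes high glycemic load days, sensor wear, and blood and stool sampling.

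What is at stake is the meaning of the signature. Agreement to one intervention does not record agreement to another. The point goes beyond recruitment paperwork, because the protocol relies on the same physician later. Section 11.3 sends clinically significant out-of-range values to the treating physician of record, and section 16.0 refers involuntarily withdrawn participants back to that physician. A physician in that position should know which study the patient entered.

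**Working it through.** No figure is involved, so the check sets the sections side by side.

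1. **What the form is said to cover.** Weight loss and brisk walking (section 8.3).

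2. **Is there a weight-loss component?** No. Stage 1 leaves the diet unchanged apart from the first meal (section 11.1). Stage 2 diets are isocaloric (section 10.0), and the food is sized to each participant's estimated energy requirement (section 11.2, selection of foods). No energy deficit is planned in either stage.

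3. **Is there a walking component?** No. Stage 1 keeps the usual daily routine. In both stages physical activity is recorded by the Fitbit and the app (sections 11.1 and 11.2.2). It is measured and not prescribed.

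4. **Could the phrase refer to a behavioral program elsewhere in the protocol?** Section 4.0 mentions the group's existing behavioral intervention, but only as something to be combined with the tailored diet in a future trial. It is not delivered here.

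5. **How do the other recruitment routes describe the study?** Section 8.1, for self-referral from the practice offices, has the provider asked whether the patient is fit to take part in the study, and names no other intervention. In section 8.2, the referring physician presents the study as one of dietary patterns and post-meal glucose. The mismatch is confined to section 8.3.

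6. **Who is affected?** The release form applies to self-referring subjects who are not patients of the institution, and the approval form follows from that release. The protocol does not say how many of the 20 participants will come this way. The range is therefore 0 of 20 (0%) to 20 of 20 (100%).

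7. **What else screens these patients?** Telephone pre-screening (section 8.3), signed consent before any measurement (sections 8.4 and 11.1), and an eligibility visit with HbA1c, demographics and calorimetry (sections 11.1 and 11.3). The questionnaire covers health characteristics and recent antibiotics (section 11.4.2), and participants are asked about food allergies before meals are prepared (section 14.0). Apart from the HbA1c and calorimetry measurements, these checks rest largely on self-report.

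**The case against.** The strongest reply is that this is a wording slip with little consequence. The form is not shown and may be correct even though the sentence describing it is not. The sentence is ungrammatical and may have been carried over from another study, although the protocol does not say so. Section 30.0 classes the study as not more than minimal risk, consent and the eligibility visit still apply, and the endpoint, equivalence margin, sample size and analysis are untouched. Most of this stands, and it limits the weight of the point. It does not remove the contradiction, because the protocol is the approved instruction and nothing in it corrects the sentence.

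A reader might infer more than the documents support:

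- **That all self-referred patients are affected.** They are not. Section 8.1 is worded correctly, and the release step in section 8.3 is limited to people from outside the institution.
- **That the physician is never told what the study involves.** Section 8.3 does not say that the form is the only information sent.
- **That the physician is the main check on the section 6.2 exclusions.** The protocol does not give the physician that task in any route, and the other screening steps listed above exist.
- **That the Aim 3 recruitment funnel is distorted** because some physicians would refuse patients unfit for brisk walking. This is conceivable, but nothing in the protocol shows that it would happen or how often.

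**Conclusion.** The point holds in a narrow form. For media self-referrals who are not patients of the institution, the sign-off described in section 8.3 names an intervention that this protocol does not contain, so it does not document clearance for the study actually done. It is a wrong statement in a safety-related step and should be corrected, but it does not threaten the design and changes no statistical result.

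The number of participants concerned is unknown, between 0 and 20 of 20. The conclusion rests on two assumptions: that the form matches the protocol's description of it, and that the undefined abbreviation used for the signatory in section 8.3 means the treating physician named in the sentence before it.

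**What to change.** Replace the phrase in section 8.3 so that the physician is asked about participation in this study, in line with section 8.1. Add a short description of what the protocol already contains: the standardized carbohydrate test breakfasts, the six days of provided low, moderate and high glycemic load meals, glucose sensor wear, blood and stool sampling, and the existing acetaminophen criterion in section 6.2. Then compare the form with the revised sentence and correct it if it carries the same wording.

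The contradiction does not require the physician to certify each section 6.2 exclusion, or the form to be extended to section 8.1. Those would be separate choices with their own paperwork.

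The cost is one sentence and one form in a minor IRB amendment. No patients, visits or tests are added.
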